	
Although acalabrutinib has not demonstrated any dose-limiting toxicities (DLTs) to date, the safety of acalabrutinib in combination with pembrolizumab in this patient population needs to be assessed and standard DLT criteria will be applied to Arm 2 of the study. Therefore an interim safety analysis will occur once 6 subjects have been successfully randomized to the combination arm (Arm 2) and have been treated a minimum of 4 weeks. Enrollment will be paused while the interim safety analysis occurs. If a DLT rate of < 33% is observed in Arm 2 (ie, DLT review is cleared), then randomization will continue to evaluate the objective response rates of pembrolizumab monotherapy and the combination of pembrolizumab and acalabrutinib (ie, up to 37 total subjects per arm). If a DLT rate of $\geq 33\%$ is observed in Arm 2, then enrollment (1:1) will continue until an additional 6 subjects are randomized to Arm 2, but with a reduced dose level for acalabrutinib (Level -1). If the DLT review is cleared in those additional 6 subjects in Arm 2 then continued enrollment will occur at Level -1 for the combination arm. If a DLT rate of $\geq 33\%$ is observed in Arm 2 at Level -1, then an additional 6 subjects will be randomized at Level -2 and assessed for DLTs. If the DLT review is cleared, continued enrollment will occur at Level -2 for the combination arm. If the DLT review is not cleared, enrollment will be halted in Arm 2.
 
Acalabrutinib treatment can continue for subjects who are tolerating therapy and not progressing. Pembrolizumab treatment is for 24 months from the date of first dose for subjects who are tolerating therapy and not progressing. Subjects who have confirmed progressive disease on the combination of pembrolizumab and acalabrutinib will discontinue study treatment while those with confirmed progressive disease in the pembrolizumab monotherapy arm will continue on pembrolizumab with the addition of acalabrutinib until a second disease progression or intolerance to therapy. For subjects who cross over to receive combination treatment, acalabrutinib treatment will begin at the next visit at which subjects are scheduled to receive pembrolizumab. The immune-related response criteria (irRECIST; Appendix 8) will be used to determine progression on this study. Pembrolizumab treatment can end for subjects with confirmed complete response (CR) if treatment has been administered for at least 24 weeks and 2 doses of pembrolizumab have been administered after confirmation of CR.
 
Refer to Appendix 4 and Appendix 5 for comprehensive lists of study assessments and their timing. A study schema is provided in Figure 3-1.

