5.0 STATISTICAL METHODS OF ANALYSIS

5.1 GENERAL CONSIDERATIONS

Descriptive statistics (including means, standard deviations, and medians for continuous variables and proportions and confidence intervals [CIs] for discrete variables) will be used to summarize data as appropriate.

For the interim safety analysis (DLT review), enrollment of 6 subjects in the combination arm for DLT review is consistent with sample sizes used in oncology studies for determination of MTD. The trial employs the standard National Cancer Institute definition of MTD (dose associated with DLT in $\leq 17\%$ of subjects). Provided the DLT review period is cleared in the combination arm and this arm is not stopped early for futility or toxicity ([Section 5.5](#)), then up to 31 subjects will be added per arm.

The sample size for this 2-arm trial was determined by a Z-test for normal approximation of binomial distribution, based on one-sided $\alpha = 0.10$, 80% power, with projected response rates of 40% in pembrolizumab/acalabrutinib arm and 18% in pembrolizumab

arm. [REDACTED] PASS version 11 was employed to conduct the sample size calculation.

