5.5 FUTILITY AND TOXICITY MONITORING

The futility and toxicity monitoring will be analyzed in the combination arm (Arm 2) only as data become available. Futility will be monitored by irDCR, which is defined as irCR, irPR, and irSD by irRECIST ([Appendix 8](#)). irDCR of at least 20% is clinically meaningful in this population. The response outcome within the 12 weeks will be used in the futility analyses. A Bayesian method ([Thall 1995](#)) will be used for futility and toxicity monitoring for the combination arm. The stopping rules are:

- $\Pr(\theta_E < 0.20 | \text{data}) > 0.95$
- Or
- $\Pr(T_E > 0.30 | \text{data}) > 0.90$

Enrollment in the combination arm will be stopped early if there is > 95% probability that the irDCR is < 20% or there is > 90% probability that the toxicity rate is higher than 30% in that arm. Where θ_E denotes the marginal response rate, assuming that θ_E follows a prior distribution of beta (a, b), where a and b represent response and nonresponse

rates (0.2, 0.8), and T_E denotes the marginal toxicity rate, assuming that T_E has a prior distribution of beta (a, b), where a and b represent toxicity and no toxicity (0.3, 0.7). The definition of toxicity will follow the same definition used for assessing DLTs (see [Section 3.7](#)) including the DLT assessment window.

The above futility and toxicity monitoring rules will be implemented once the first 10 subjects have been evaluated in the combination arm and will use safety data as they become available. The corresponding stopping boundaries for the futility monitoring are: enrollment will be stopped early due to futility if (number of subjects with irDCR/number subjects evaluated) \leq 0/(10-15), 1/(16-23), 2/(24-30) and 3/(31-37). The corresponding stopping boundaries for toxicity monitoring are listed in [Table 5-1](#).

The operating characteristics of the design are presented in [Table 5-2](#). Multc Lean software V2.1 was used for the design.

Table 5-1. Stopping Boundaries for Toxicity Monitoring

	Stop enrolling if there are this many DLTs total:
No. Subjects (inclusive)	# Toxicities (inclusive)
1-9	Never stop with this many subjects
10-12	6-12
13-14	7-14
15-17	8-17
18-20	9-20
21-23	10-23
24-25	11-25
26-28	12-28
29-31	13-31
32-34	14-34
35-36	15-36
37	Always stop due to maximum sample size

Table 5-2. Operating Characteristics of the Design

irDCR	Toxicity rate	Probability of early stop	Average # of subjects treated
0.2	0.1	0.23	32.1
0.2	0.3	0.41	28.2
0.2	0.5	0.95	14.8

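### After 6 or more DLTs in the first 12 Arm 2 subjects with both dose cohorts failing, the synopsis orders six subjects at Level -2 while Table 5-1 orders enrolment stopped

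*Protocol*

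**What the plan says.** **Dose-level review (Synopsis, Study Design).** Six Arm 2 subjects are reviewed after at least 4 weeks of treatment. If the DLT rate is 33% or more, that is 2 or more of 6, "then enrollment (1:1) will continue until an additional 6 subjects are randomized to Arm 2, but with a reduced dose level" of acalabrutinib (Level -1). If Level -1 also shows 33% or more, "then an additional 6 subjects will be randomized at Level -2 and assessed for DLTs". The review itself closes the arm only after Level -2 fails: "If the DLT review is not cleared, enrollment will be halted in Arm 2".

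**Arm-level monitoring (Section 5.5).** The futility and toxicity rules apply to Arm 2 and "will be implemented once the first 10 subjects have been evaluated in the combination arm". Enrolment stops if there is more than a 90% "probability that the toxicity rate is higher than 30% in that arm". Toxicity has the same definition and window as a DLT. The column heading of Table 5-1 reads "Stop enrolling if there are this many DLTs total", and for 10 to 12 subjects the entry is 6 to 12. The table runs from subject 1 to subject 37. Nothing restricts it to one dose level or resets the count after a dose reduction.

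**The link between them.** Section 5.1 states: "Provided the DLT review period is cleared in the combination arm and this arm is not stopped early for futility or toxicity", up to 31 subjects are added per arm. The Statistical Methods row of the synopsis says much the same and refers to Section 5.5.

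**The concern.** By subject 12 of Arm 2 both rules are active on the same DLTs. The synopsis looks only at the six subjects at Level -1, while Table 5-1 looks at all 12, including those at the abandoned starting dose. With 3 of 6 followed by 3 of 6, the synopsis orders six more subjects and Table 5-1 orders that none be enrolled.

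The linking sentence in Section 5.1 does not settle this. It concerns the expansion after a cleared review, and here the review has failed.

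At stake is subject safety. Followed literally, the synopsis randomises six more subjects to the combination after the protocol's own toxicity boundary has been crossed. These are two stated enrolment rules that give opposite orders, so this is more than detail that could be left to the SAP.

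**Working it through.** **1. Reproduce the plan's figures.** Section 5.5 gives a beta(0.3, 0.7) prior, a 30% limit and a 0.90 threshold. With x DLTs in n subjects the posterior is beta(0.3 + x, 0.7 + n − x). At n = 12:

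- x = 6: Pr(rate > 30%) under beta(6.3, 6.7) = 0.913, above 0.90, so stop.
- x = 5: Pr(rate > 30%) under beta(5.3, 7.7) = 0.780, so continue.

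This matches Table 5-1. All its other boundaries, and the futility boundaries, also reproduce. Exact recursion with a look after every subject from the tenth, and response independent of toxicity, gives early-stop probabilities of 0.231, 0.415, 0.950, 0.049, 0.276 and 0.938. Table 5-2 has 0.23, 0.41, 0.95, 0.05, 0.28 and 0.94, and its average sample sizes match too. The table therefore rests on one cumulative count from the first Arm 2 subject.

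**2. Which outcomes conflict.** Let X be the DLTs among six at the starting dose and Y those among six at Level -1. The synopsis orders Level -2 when X ≥ 2 and Y ≥ 2, which is 5 × 5 = 25 pairs. Table 5-1 orders a stop when X + Y ≥ 6. Only 2+2, 2+3 and 3+2 fall below 6, so 22 of the 25 pairs conflict.

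**3. How often.** The protocol gives no DLT rate for the combination, so the rates p₁ (starting dose) and p₂ (Level -1) are assumptions, with X ~ Bin(6, p₁) and Y ~ Bin(6, p₂) independent.

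P(conflict) = P(X ≥ 2)·P(Y ≥ 2) − P(2+2) − P(2+3) − P(3+2)

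Example with p₁ = 30%, p₂ = 20%:

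- Both cohorts fail: 0.580 × 0.345 = 0.200.
- Pairs without conflict: 0.324 × 0.246 + 0.324 × 0.082 + 0.185 × 0.246 = 0.152.
- Conflict: 0.200 − 0.152 = 0.048. Given that both fail: 0.048 / 0.200 = 0.24.

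| Assumed p₁ / p₂ | Conflict, all trials | Conflict, given Level -2 is ordered |
|---|---|---|
| 20% / 10% | 0.35% | 9% |
| 20% / 20% | 1.8% | 15% |
| 30% / 10% | 1.1% | 17% |
| 30% / 20% | 4.8% | 24% |
| 40% / 20% | 9.4% | 36% |
| 40% / 30% | 20% | 44% |
| 50% / 30% | 30% | 57% |

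**4. Effect on Table 5-2.** The same recursion was run with the six-subject reviews added, the arm-wide count kept and 30% toxicity at every level. Early stop is then 0.47 at irDCR 20% and 0.34 at irDCR 30%, against 0.41 and 0.28 in the table. The mean number treated is 26.9 and 29.8, against 28.2 and 31.3.

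**The case against.** **The stop is the natural reading.** Section 5.5 states an unconditional arm-level stop, and a dose step needs an arm that is open. Sections 5.1 and the synopsis let that stop block an arm whose review has cleared, so it would be odd to let an arm with a failed review go past it. This largely stands and decides the direction of the fix. It remains an inference, because both linking sentences concern the expansion.

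**The conflict is rare unless toxicity is high, and then stopping is right.** This stands. Unconditional rates of 20-30% need 40-50% at the starting dose and 30% at Level -1. The conditional column is still relevant, because a de-escalation rule matters only once cohorts have failed.

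**Little is lost by stopping.** This also stands. Level -2 (50 mg BID) has the same daily total as Level -1 (100 mg QD), namely 100 mg (Table 3-2), and Level -1 has just failed.

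**Other text may settle it.** The schema in Figure 3-1 is not shown and some synopsis text is redacted, so this cannot be excluded. The visible rules still give opposite orders.

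**Stronger readings a reader might infer.**

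- That pooling across doses is an error and Table 5-1 should count each level separately. The documents do not support this: the rule is written for the arm. Per-level counting would also weaken protection. At 50% toxicity on every level the mean treated would be 19.6 and 20.8, against 14.8 and 15.5 in Table 5-2.
- That the rules also clash when Level -1 clears, for example 5 of 6 then 1 of 6. There Section 5.1 lets the Section 5.5 stop prevail over the expansion.
- That Table 5-2 is wrong. It is correct for the Section 5.5 rule alone.

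**Conclusion.** The point holds for one situation: the starting dose and Level -1 both fail their reviews, with at least 6 DLTs in the first 12 Arm 2 subjects. The synopsis then orders Level -2, Table 5-1 orders a stop, and the text gives the stop precedence only for the expansion. At modest assumed DLT rates (20-30%, then 10-20%) this is 0.35% to 4.8% of trials. Across all the assumed pairs it is 9% to 57% of trials in which Level -2 is ordered.

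The figures assume independent outcomes and exactly 12 evaluated subjects. Replacements under Section 3.3.3 could move n to 13 or 14, where the boundary is 7; that shifts the threshold without removing the conflict. A reader might infer that the safety design is unsound. The documents do not support that: the boundaries are computed correctly, and the sensible resolution is already suggested by Section 5.1. It should be written down, because the other reading enrols six subjects when the pooled Pr(rate > 30%) is at least 0.91.

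**What to change.** Add to the synopsis (Study Design) and to Section 5.5: Table 5-1 counts all evaluated Arm 2 subjects and their DLTs across dose levels, and a Table 5-1 stop overrides any step to a lower acalabrutinib dose level.

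Add a note under Table 5-2 that its figures describe the Section 5.5 rule without the DLT review. With the review, and 30% toxicity at every level, early stop is about 0.47 and 0.34 (irDCR 20% and 30%) rather than 0.41 and 0.28.

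The boundaries, the 30% and 0.90 thresholds and the maximum of 37 per arm stay as they are. The cost is that in rare cases Level -2 is not tested. Per-level counting would also remove the conflict, but it trades away protection and is not recommended.

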3.7 ASSESSMENT OF DOSE-LIMITING TOXICITY (DLT)

As outlined in [Section 3.0](#), DLT review will be applied to Arm 2 as the combination of acalabrutinib plus pembrolizumab has not been evaluated before, therefore an interim safety analysis will occur once 6 subjects have been successfully randomized to the combination arm (Arm 2) and have been treated a minimum of 4 weeks. Enrollment will be paused while the interim safety analysis occurs.

A DLT will be defined as the occurrence of any of the following study-drug-related AEs (note: AEs clearly related to disease progression or the subject's current medical history and associated comorbidities will not be considered DLTs):

1. Grade 4 vomiting or diarrhea
2. Grade 3 nausea, vomiting, or diarrhea lasting for > 72 hours
3. Other Grade ≥ 3 toxicities (Note: Transient Grade 3/4 laboratory abnormalities that are not clinically significant will not be considered DLTs)
4. Dosing delay due to toxicity for > 21 consecutive days.

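### Table 5-2 is presented as the operating characteristics of the design, but its figures hold only for the Section 5.5 boundaries without the six-subject DLT review

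*Protocol*

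**What the plan says.** Section 5.5 sets Bayesian stopping rules for Arm 2. On the toxicity side, enrollment stops when there is more than 90% "probability that the toxicity rate is higher than 30% in that arm", with a beta prior "where a and b represent toxicity and no toxicity (0.3, 0.7"). Toxicity is the DLT event of Section 3.7, over the same assessment window. The futility limits on irDCR are "0/(10-15), 1/(16-23), 2/(24-30) and 3/(31-37"). Both rules "will be implemented once the first 10 subjects have been evaluated in the combination arm", and for 1 to 9 subjects Table 5-1 reads "Never stop with this many subjects". The section then says "The operating characteristics of the design are presented in" Table 5-2, which gives the probability of early stop and the average number treated at irDCR 0.2 and 0.3 and toxicity 0.1, 0.3 and 0.5.

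There is also an earlier decision point. Section 3.7 says "therefore an interim safety analysis will occur once 6 subjects have been successfully randomized to the combination arm (Arm 2"). Under Study Design in the synopsis, the review is cleared only if the observed DLT rate is below 33%. Otherwise Arm 2 moves to acalabrutinib Level -1, then to Level -2, and is halted if Level -2 also fails. After clearance, Section 5.1 says "then up to 31 subjects will be added per arm". Since 6 + 31 = 37, the review subjects are part of the 37 in Tables 5-1 and 5-2.

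**The concern.** One toxicity rate drives two rules: the review at six subjects and the Table 5-1 boundary from ten. A dose reaches the Table 5-1 boundary only if its first six subjects had at most one DLT. Operating characteristics of the whole design would have to reflect that, and nothing in Section 5.5 says that the table sets the review aside or is conditional on clearing it.

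Table 5-2 is the only quantitative statement of how the stopping rules perform. An ethics committee or sponsor team could use it in two ways: to judge how many subjects a toxic starting dose would reach, or to judge how likely such a dose is to be caught during the 31-subject expansion. If the review is missing from the table, it answers neither question, and the errors run in opposite directions.

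**Working it through.** **Inputs.** From Section 5.5: priors beta(0.2, 0.8) for irDCR and beta(0.3, 0.7) for toxicity; stop if Pr(irDCR < 0.20) > 0.95 or Pr(toxicity > 0.30) > 0.90; first look at 10 subjects; maximum 37. From the synopsis and Section 3.7: review at 6 subjects, cleared if the DLT rate is below 33%. Since 2/6 = 33.3%, clearance means 0 or 1 DLT.

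**Step 1: boundaries.** With t toxicities in n subjects the posterior is beta(0.3 + t, 0.7 + n - t). At n = 10, t = 5 gives Pr(toxicity > 0.30) = 0.890 (continue) and t = 6 gives 0.969 (stop), as printed. For irDCR, one success in 15 gives Pr(irDCR < 0.20) = 0.948 (continue) and one in 16 gives 0.958 (stop), as printed. All rows of Table 5-1 and all futility limits are returned in this way.

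**Step 2: Table 5-2 without the review.** Exact recursion over counts of responses and toxicities, the two taken as independent, with a look after every subject from n = 10 and no action at n = 6:

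| irDCR | Toxicity | Printed stop / average N | Computed, no review |
|---|---|---|---|
| 0.2 | 0.1 | 0.23 / 32.1 | 0.231 / 32.08 |
| 0.2 | 0.3 | 0.41 / 28.2 | 0.415 / 28.19 |
| 0.2 | 0.5 | 0.95 / 14.8 | 0.950 / 14.83 |
| 0.3 | 0.1 | 0.05 / 35.9 | 0.049 / 35.87 |
| 0.3 | 0.3 | 0.28 / 31.3 | 0.276 / 31.25 |
| 0.3 | 0.5 | 0.94 / 15.5 | 0.938 / 15.50 |

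The match on all six rows shows that the review was left out.

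**Step 3: probability that the review is not cleared.** P(at least 2 of 6) = 1 - (1 - p)^6 - 6p(1 - p)^5.
- p = 0.1: 0.114
- p = 0.3: 0.580
- p = 0.5: 1 - 1/64 - 6/64 = 57/64 = 0.891

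**Step 4: the same recursion with the review at n = 6.** The starting-dose column counts leaving the dose at the review as 6 subjects treated.

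| irDCR | Toxicity | Printed stop / average N | Given a cleared review | Average N at starting dose |
|---|---|---|---|---|
| 0.2 | 0.3 | 0.41 / 28.2 | 0.29 / 31.2 | 16.6 |
| 0.3 | 0.3 | 0.28 / 31.3 | 0.12 / 34.8 | 18.1 |
| 0.2 | 0.5 | 0.95 / 14.8 | 0.82 / 22.7 | 7.8 |
| 0.3 | 0.5 | 0.94 / 15.5 | 0.78 / 24.6 | 8.0 |

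At toxicity 0.1 the figures given clearance barely differ from print (0.23 / 32.1 and 0.05 / 35.9).

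**Step 5: toxicity boundary alone, futility switched off.**

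| Toxicity | No review | Given a cleared review |
|---|---|---|
| 0.3 | 0.24 | 0.08 |
| 0.4 | 0.66 | 0.37 |
| 0.5 | 0.94 | 0.77 |

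The probability of leaving the starting dose by either the review or the toxicity boundary is 0.61 at toxicity 0.3 (boundary alone 0.24) and 0.975 at 0.5 (boundary alone 0.935).

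**Step 6: the whole arm over three dose levels.** This needs two assumptions that the protocol does not supply: the toxicity rate at each level (taken as equal) and how subjects from failed levels count in Section 5.5. Results are stop probability / average N for irDCR 0.2, then 0.3.
- Counts restart at each level, with up to 37 at the level that clears: toxicity 0.3, 0.43 / 31.8 and 0.29 / 34.7; toxicity 0.5, 0.95 / 21.0 and 0.94 / 21.6. Stop probabilities stay within 0.02 of print; average N rises by 3.4 to 6.2.
- Counts pooled, 37 in total: toxicity 0.3, 0.47 / 26.9 and 0.34 / 29.8; toxicity 0.5, 0.96 / 14.3 and 0.95 / 14.9. The toxicity 0.3 stop probabilities rise by 0.06; the 0.5 rows are close to print.

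**The case against.** The best defence is that, within Section 5.5, the design means the Bayesian monitoring design just defined. The next sentence names the software used for it, Table 5-1 shows openly that nothing happens before ten subjects, and Section 5.1 treats the DLT review and Section 5.5 stopping as separate conditions. On that reading the table is correct for its section and lacks only a label. Part of this stands: there is no arithmetic error, and the boundaries are right. But no text limits the table to those rules, and the six review subjects lie within the 37 that it describes.

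A reader might infer something stronger: that the trial protects subjects less well than stated. The documents do not support this. The review adds a stopping point for the starting dose, so overall protection there rises. The lower stopping rates apply only to doses that have already passed the review, and Table 5-2 does not claim to be conditional on that. It would also be wrong to set the 8% at toxicity 0.3 (toxicity boundary alone, after clearance) against the printed 28-41%, which combine futility and toxicity. The like-for-like figure is 24%. Moreover, 0.30 is the rule's own threshold, so infrequent stopping there is not in itself a failure; the results at 0.4 and 0.5 are more informative.

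Finally, a failed first review lowers the dose and does not stop the arm. Whole-arm stop probabilities therefore move little, and no single correct whole-arm table can be computed from the protocol as written.

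**Conclusion.** The point holds as one about what Table 5-2 describes. Its six rows are the properties of the Section 5.5 boundaries without the DLT review, yet they are presented as those of the design. At toxicity 0.3 and 0.5 the table overstates average exposure at the starting dose by roughly 7 to 13 subjects (15.5 - 8.0 = 7.5 up to 31.3 - 18.1 = 13.2). It also overstates by 0.12 to 0.16 the chance that a dose which has cleared the review is later stopped early. At toxicity 0.1 the conditional figures are essentially unchanged, although 11% of trials would still leave the starting dose at the review.

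These results assume independent response and toxicity outcomes, a look after every subject from the tenth, and 2 of 6 counted as not cleared. If 2 of 6 were cleared, the non-clearance probabilities would still be 0.256 at toxicity 0.3 and 0.656 at 0.5. The whole-arm figures also rest on the equal-toxicity and counting assumptions in step 6.

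**What to change.** Either of two changes would settle it.

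1. Recompute Table 5-2 with the review at n = 6 included. State in Section 5.5 how subjects from failed dose levels are counted. For each toxicity rate, show the probability that the review is not cleared, the probability of early stop and average N given clearance, and the average number treated at the starting dose. A row at toxicity 0.4 would help, because 0.30 is the rule's threshold.
2. Keep the printed figures and relabel the table *Section 5.5 boundaries only, without the DLT review*.

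The first costs a short calculation and a replacement table; the second costs one line. Neither needs more subjects or alters a boundary, a dose or a clinical rule.
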